Safety, Tolerability, and Pharmacokinetics of Lasmiditan in Healthy Chinese Subjects

Rationale:

Lasmiditan is a highly selective and potent agonist of the 5-hydroxytryptamine (5-HT)_{1F} receptor that is being developed as a neurally acting treatment for migraine.

This study is the first clinical evaluation of single and multiple oral doses of lasmiditan in Chinese subjects, and will facilitate subsequent clinical trials in Chinese patients. Characterization of the safety and pharmacokinetics (PK) of lasmiditan in Chinese subjects is essential for further clinical development in China.

Objectives/Endpoints:

Objectives	Endpoints

Primary
 
To evaluate the PK of single and multiple doses of lasmiditan in healthy Chinese subjects.
	
AUC(0-∞) [single-dose only], AUC(0-τ) C_{max}, and t_{max}.

Secondary
 
To explore the safety and tolerability of single and multiple oral doses of lasmiditan in healthy Chinese subjects.
	
Incidence of SAEs and TEAEs.

Abbreviations: AUC(0-∞) = area under the concentration versus time curve from time zero extrapolated to infinity; AUC(0-τ) = area under the concentration versus time curve over a dosing interval; C_{max} = maximum observed plasma concentration; PK = pharmacokinetics; SAE = serious adverse event; TEAE = treatment-emergent adverse event; t_{max} = time of maximum observed plasma concentration.

Summary of Study Design:

Study H8H-MC-LAIC is an investigator- and subject-blinded, randomized, placebo-controlled study in healthy Chinese subjects. The study will evaluate the safety, tolerability, and PK of lasmiditan following single and multiple oral doses of 50, 100, and 200 mg.

Treatment Arms and Planned Duration for an Individual Subject:

All subjects will participate in a screening visit up to 28 days prior to study drug dosing.

Subjects will be enrolled into 1 of 3 cohorts. All subjects will be admitted to the clinical research unit (CRU) on Day -1. Each subject will receive a single dose of lasmiditan or placebo on Day 1 and multiple once-daily doses of lasmiditan or placebo on Days 4 to 10 of the study. Subjects will discharge from the CRU on Day 12 and attend a follow-up visit approximately 7 to 10 days following their final dose of investigational product (IP).

The planned study duration for each subject will be up to 50 days.

Number of Subjects:

Up to 36 subjects (12 subjects per cohort) may be enrolled and randomized so that approximately 8 subjects per cohort, who receive lasmiditan, complete the study.

Statistical Analysis:

Safety parameters that will be assessed include safety lab parameters and vital signs. The parameters will be listed and summarized using descriptive statistics as appropriate.

Pharmacokinetic parameter estimates for lasmiditan and metabolites M7, M8, (S,R)-M18, and (S,S)-M18 will be calculated by standard noncompartmental methods of analysis. Trough concentrations of lasmiditan and its metabolites will be evaluated graphically and/or descriptively for achievement of steady-state.

Log-transformed C_{\max} and AUC parameters (AUC[0- ∞] for Day 1 and AUC[0- τ] for Day 10) will be evaluated using a power model (where the log of the dose will be an explanatory variable) to estimate ratios of dose-normalized geometric means and the corresponding 90% confidence intervals (CIs). The estimated ratio between the highest and lowest doses will be used to assess dose proportionality. The intersubject coefficient of variation will be derived.

2. Schedule of Activities

Study Schedule Protocol H8H-MC-LAIC

Procedure	Screening	Day									FU/ ED	Comments	
	D-28 to D-2	-1	1	2	3	4	5 to 9	10	11	12			
Informed Consent	X												
Subject Admission to CRU		X											
Subject Discharge from CRU										X			
Lasmiditan or Placebo Administration			X			X	X	X					Approximately 72 hours between the first (D1) and second (D4) lasmiditan/placebo doses.
Medical History	X												
Urine Drug Screen	X	X											
Alcohol test	X	X											
Height	X												
Weight	X	X									X		
Single Vital Signs (supine)	X		P, 0.5, 1, 2, 2.5, 3, 4, 6, 8, 12 h	24 h		P, 0.5, 1, 2, 2.5, 3, 4, 6, 8, 12 h	24 h (D5)	P, 0.5, 1, 2, 2.5, 3, 4, 6, 8, 12 h	24 h		X		Time points relative to dosing on D1, D4, and D10. Vital signs may be performed at other times as clinically indicated, determined by the investigator.
Single Orthostatic Vital Signs	X		P, 2 h	24 h		P, 2 h	24 h (D5)	P, 2 h	24 h				Time points relative to dosing on D1, D4, and D10. Vital signs may be performed at other times as clinically indicated, determined by the investigator.
Clinical Laboratory Tests	X	X	P			P		P		X	X		See Appendix 2 , Clinical Laboratory Tests, for details.

Procedure	Screening	Day										FU/ ED	Comments	
		-1	1	2	3	4	5 to 9	10	11	12				
	D-28 to D-2													FU approximately 7 to 10 days post final dose.
HIV/Hepatitis Tests	X													See Appendix 2 , Clinical Laboratory Tests, for details.
Pregnancy Test	X	X										X		Female subjects of childbearing potential only. Serum pregnancy test will be performed at screening. Urine pregnancy test will be performed at admission and at FU.
FSH	X													Postmenopausal females only.
Physical Examination	X	X			X						X	X		After screening, medical assessment only performed to include medical review and targeted examination, as appropriate.
Single 12-Lead ECG	X		P, 2, 4 h	24 h		P, 2, 4 h	24 h (D5)	P, 2, 4 h	24 h			X		Time points relative to dosing on D1, D4, and D10.
C-SSRS and Lilly Self-Harm Supplement	X	X									X	X		C-SSRS “Baseline” questionnaire to be used at screening, all other time points use “Since Last Visit” questionnaire.
Adverse Event Review		X	X	X	X	X	X	X	X	X	X	X		
Plasma Samples for Lasmiditan and Metabolite Pharmacokinetics			P, 0.5, 1, 1.5, 2, 2.5, 3, 4, 6, 8, 12 h	24, 36 h	48 h	P	P	P, 0.5, 1, 1.5, 2, 2.5, 3, 4, 6, 8, 12 h	24, 36 h	48 h				Time points relative to dosing on D1, D4, and D10. Predose samples to be taken on D5 to D9 for assessment of steady-state.

Abbreviations: CRU = clinical research unit; C-SSRS = Columbia-Suicide Severity Rating Scale; D = Day; ECG = electrocardiogram; ED = early discontinuation; FSH = follicle-stimulating hormone; FU = follow-up; HIV = human immunodeficiency virus; P = predose.

Note: if multiple procedures take place at the same time point, the following order of the procedure should be use: ECG, vital signs, and venipuncture.

3. Introduction

Lasmiditan (LY573144) is being developed by Eli Lilly and Company (Lilly) for the acute treatment of migraine attacks, with or without aura, in adults. This molecule has also been developed by CoLucid Pharmaceuticals, Inc. as COL-144. Full details of the preclinical and clinical safety and tolerability data are contained in the Investigator's Brochure (IB).

3.1. Study Rationale

Lasmiditan is a highly selective and potent agonist of the 5-hydroxytryptamine (5-HT)_{1F} receptor that is being developed as a neurally acting treatment for migraine.

This study is the first clinical evaluation of single and multiple doses of lasmiditan in Chinese subjects, and will facilitate subsequent clinical trials in Chinese patients. Characterization of the safety and pharmacokinetics (PK) of lasmiditan in Chinese subjects is essential for further clinical development in China.

3.2. Background

Lasmiditan has a chemical structure and pharmacological profile that is distinct from triptans, which are the current standard of care for the treatment of acute migraine. It does not contain the indole group found in all triptans, but instead has a pyridinoyl-piperidine scaffold that is unique to antimigraine medications. Lasmiditan is a low-molecular-weight agonist of the 5-HT_{1F} receptor with a nonvascular and primarily neural mechanism of action. It has a high affinity for the human 5-HT_{1F} receptor and a >470-fold selectivity for the human 5-HT_{1F} receptor relative to the 5-HT_{1B} receptor.

Lasmiditan doses of 0.1 to 400 mg have been evaluated in healthy subjects or patients with migraine across completed Phase 1, 2, and 3 clinical studies. Cumulatively through 05 March 2018, a total of 3948 subjects/patients have received lasmiditan. The most frequently reported lasmiditan treatment-emergent adverse events (TEAEs) in the 2 Phase 3 placebo-controlled studies, in which patients treated 1 migraine attack with oral lasmiditan (50, 100, or 200 mg) or placebo, were dizziness, paresthesia, somnolence, fatigue, lethargy, and nausea, and the majority were mild or moderate in severity. Safety and tolerability in healthy subjects were similar up to the highest dose of 400 mg administered as a single and multiple (once daily for 7 days) dose, with tiredness, drowsiness, dizziness, and paresthesia being the most frequently reported adverse events (AEs). The majority of these were mild in severity, and none were severe.

Following dose administration of a single oral tablet to healthy subjects, lasmiditan was absorbed with a median t_{max} of 1.5 to 2.5 hours, and rapidly eliminated with a mean $t_{1/2}$ of approximately 4 hours. Over the clinical dose range of 50 to 200 mg, the mean estimates of lasmiditan C_{max} and $AUC(0-\infty)$ increased in a dose-dependent manner that was approximately linear with dose.

Following oral dosing with lasmiditan, up to 16 metabolites, including 3 major metabolites (M7, M8, and M18), were detected in human plasma and urine. These metabolites lacked significant pharmacological activity at the 5-HT_{1F} receptor and were generally considered to be pharmacologically inactive. The relative proportions of metabolites to intact lasmiditan

remained reasonably constant throughout the oral dose range studied and their PK was approximately linear. The half-life of the metabolites ranged from approximately 4.5 to 21 hours.

The characterization of lasmiditan PK in Asian subjects has been limited. Therefore, it is not known whether there are PK differences between subjects of Asian descent, relative to the overall population.

3.3. Benefit/Risk Assessment

Oral doses of lasmiditan up to the highest single and multiple oral dose given (400 mg) were well tolerated in healthy subjects, with no drug-related serious adverse events (SAEs) or withdrawals due to AEs as of 05 March 2018. Lasmiditan caused no significant QT prolongation either at 100 or 400 mg, and no clinically significant changes in clinical laboratory data. Lasmiditan has been associated with transient lowering of heart rate (on average about 8 to 12 bpm). Throughout this study, vital signs will be closely monitored for effects of lasmiditan on heart rate. Although nervous system disorders were commonly reported as AEs, especially at higher dose levels, they were generally mild or moderate in intensity. Dosing of subjects in this study will be conducted in an inpatient setting, and subjects will be monitored in-house for at least 48 hours after the last dose of investigational product (IP).

There is no anticipated therapeutic benefit for the subjects.

More information about the known and expected benefits, risks, SAEs, and reasonably anticipated AEs of lasmiditan are to be found in the IB.

4. Objectives and Endpoints

Table LAIC.1 shows the objectives and endpoints of the study.

Table LAIC.1. Objectives and Endpoints

Objectives	Endpoints

Primary To evaluate the PK of single and multiple doses of lasmiditan in healthy Chinese subjects.
	AUC(0-∞) [single-dose only], AUC(0-τ), C _{max} , and t _{max} .

Secondary To explore the safety and tolerability of single and multiple oral doses of lasmiditan in healthy Chinese subjects.
	Incidence of SAEs and TEAEs.

Exploratory To evaluate the PK of metabolites M7, M8, (S,R)-M18, and (S,S)-M18 in healthy Chinese subjects.
	AUC(0-∞), C _{max} , and t _{max} .

Abbreviations: AUC(0-∞) = area under the concentration versus time curve from time zero extrapolated to infinity; AUC(0-τ) = area under the concentration versus time curve over a dosing interval; C_{max} = maximum observed plasma concentration; PK = pharmacokinetics; SAE = serious adverse event; TEAE = treatment-emergent adverse event; t_{max} = time of maximum observed plasma concentration.

5. Study Design

5.1. Overall Design

This study is a Phase 1, investigator- and subject-blinded, randomized, placebo-controlled study in healthy Chinese subjects.

Subjects will be enrolled into 1 of 3 cohorts and receive single and multiple doses of lasmiditan or placebo in a parallel design. Each cohort will comprise 12 subjects (10 lasmiditan:2 placebo) and will be assigned the following doses:

- Cohort 1 = 50 mg lasmiditan (or placebo)
- Cohort 2 = 100 mg lasmiditan (or placebo)
- Cohort 3 = 200 mg lasmiditan (or placebo)

Subjects will be evaluated for study eligibility ≤ 28 days prior to enrollment. Subjects who fulfill the eligibility criteria will be admitted to the clinical research unit (CRU) on Day -1 (the day before their first dose of lasmiditan or placebo; Section 2).

After randomization on Day 1, IP (lasmiditan or placebo) will be administered orally once on the morning of Day 1 after an overnight fast of at least 8 hours. Following a period of at least 72 hours without IP dosing, subjects will receive multiple once-daily oral doses of IP on Days 4 to 10 (7 days of dosing), after overnight fasts of at least 8 hours prior to each dose. The doses of lasmiditan administered on Days 4 to 10 will be the same dose as that administered on Day 1 for each subject.

Subjects will be discharged from the CRU on Day 12 following completion of all scheduled procedures, as defined in the Schedule of Activities (Section 2), and will attend a follow-up visit approximately 7 to 10 days following final oral dose of IP.

The planned study duration for each subject will be up to 50 days.

Blood samples will be collected for PK analysis. Safety and tolerability will be assessed throughout the study by means of AE review, physical examinations, vital sign measurements, 12-lead electrocardiograms (ECGs), clinical laboratory tests, and Columbia-Suicide Severity Rating Scale (C-SSRS).

Study governance considerations are described in detail in [Appendix 3](#).

5.2. Number of Participants

Up to 36 subjects (12 subjects per cohort) may be enrolled and randomized so that approximately 8 subjects per cohort, who receive lasmiditan, complete the study. For purposes of this study, a subject completes the study when all scheduled procedures shown in the Schedule of Activities (Section 2) have been finished.

5.3. End of Study Definition

End of the study is the date of the last visit or last scheduled procedure shown in the Schedule of Activities (Section 2) for the last subject.

5.4. Scientific Rationale for Study Design

A subject- and investigator-blinded, randomized, and placebo-controlled design has been chosen to minimize bias in the safety and tolerability objective of this study.

Single and repeated doses of 50, 100, and 200 mg lasmiditan are considered the planned clinical doses.

Pharmacokinetic sampling time points have been selected to generate PK profiles sufficient to fulfill the study objectives.

Conducting the study in healthy subjects mitigates the potential confounding effects of the disease state, other medical conditions, and concomitant medications in patients. Conducting this study in Chinese subjects will provide PK data for evaluation on ethnic sensitivity of lasmiditan. In addition, it will support the inclusion of Chinese subjects in a future global Phase 3 study with lasmiditan.

It is not considered necessary to conduct safety data reviews of previous cohorts (lower dose levels) prior to dosing the next cohort. The relative dosing of cohorts (parallel or sequential) will therefore be at the discretion of the investigator.

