7.1. Treatment Administered

This study involves a comparison of single (Day 1) and repeated (Days 4 to 10) doses of 50, 100, and 200 mg lasmiditan administered orally, with placebo.

Table LAIC.2 shows the treatment regimens at for each cohort.

Table LAIC.2. Treatments Administered

Cohort	Dose level	Number of tablets administered per dose
1	50 mg lasmiditan or placebo	1 x 50-mg tablet
2	100 mg lasmiditan or placebo	1 x 100-mg tablet
3	200 mg lasmiditan or placebo	2 x 100-mg tablet

Tablets of lasmiditan or placebo will be orally administered with approximately 240 mL of room-temperature water in the morning of each dosing day, in a sitting position. Subjects will not be allowed to lie supine for 2 hours after dosing, unless clinically indicated or for study procedures.

The investigator or designee is responsible for:

- explaining the correct use of the IP(s) to the site personnel
- verifying that instructions are followed properly
- maintaining accurate records of IP dispensing and collection
- and returning all unused medication to Lilly or its designee at the end of the study

Note: In some cases, sites may destroy the material if, during the investigative site selection, the evaluator has verified and documented that the site has appropriate facilities and written procedures to dispose of clinical materials.

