7.2. Method of Treatment Assignment

Assignment to treatment groups will be determined by a computer-generated random sequence using an interactive web-response system (IWRS). The IWRS will be used to assign a blister containing double-blind IP to each subject.

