7.3. Blinding

The investigator and subjects will be blinded to the study treatment assignments.

Blinding will be maintained throughout the conduct of the study as described in the separate Blinding Plan.

Emergency unblinding for AEs may be performed through the IWRS. This option may be used ONLY if the subject's well-being requires knowledge of the subject's treatment assignment. All unblinding events are recorded and reported by the IWRS.

If a subject's study treatment assignment is unblinded, the subject must be discontinued from the study, unless the investigator obtains specific approval from a Lilly clinical pharmacologist (CP) or clinical research physician (CRP) for the study participant to continue in the study. During the study, emergency unblinding should occur only by accessing the study subject's emergency code.

In case of an emergency, the investigator has the sole responsibility for determining if unblinding of a subject's treatment assignment is warranted for medical management of the event. The subject's safety must always be the first consideration in making such a determination. If the investigator decides that unblinding is warranted, it is the responsibility of the investigator to promptly document the decision and rationale and notify Lilly as soon as possible.

Upon completion of the study, all codes must be returned to Lilly or its designee.

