9.2. Treatment of Overdose

For the purposes of this study, an overdose of lasmiditan is considered any dose higher than the dose assigned through randomization.

There is no specific antidote for lasmiditan. In the event of overdose, the subject should receive appropriate supportive care and AEs should be documented.

Refer to the IB for further information.

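### Is dose level randomised in this study, and must the 200:50 mg ratio be labelled a non-randomised comparison if it is not?

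*Protocol*

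**What the plan says.** Protocol 5.1 states: "Subjects will be enrolled into 1 of 3 cohorts and receive single and multiple doses of lasmiditan or placebo in a parallel design". Each cohort has 10 lasmiditan and 2 placebo subjects and is given one dose: 50, 100 or 200 mg. The same section places random allocation immediately before the first dose: "After randomization on Day 1, IP (lasmiditan or placebo) will be administered orally once on the morning of Day 1". Protocol 5.2 gives the total: "Up to 36 subjects (12 subjects per cohort) may be enrolled and randomized". Protocol 5.4 says that no safety review is needed between cohorts, and so "The relative dosing of cohorts (parallel or sequential) will therefore be at the discretion of the investigator".

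On allocation, Protocol 7.2 says: "Assignment to treatment groups will be determined by a computer-generated random sequence using an interactive web-response system (IWRS"). Protocol 7.3 says: "The investigator and subjects will be blinded to the study treatment assignments", and refers to a separate Blinding Plan for the detail. In Protocol 7.1, Table LAIC.2 gives one tablet per dose in the first two cohorts and "2 x 100-mg tablet" in the third, placebo included. Protocol 9.2 defines its term by reference to allocation: "an overdose of lasmiditan is considered any dose higher than the dose assigned through randomization".

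SAP section 5 repeats the design text of 5.1. SAP section 6 lists placebo and the three doses as table columns, and SAP section 8 pools placebo over cohorts. SAP 9.3.2 fits a power model of log PK on log dose and reports the 200:50 mg ratio of dose-normalised geometric means with a 90% confidence interval. SAP 9.4.8 plans no inferential safety analysis.

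**The concern.** Two readings seem possible. In one, the web-response system allocates subjects to dose as well as to lasmiditan or placebo. Protocol 9.2 says as much, and 7.2 can be read that way. In the other, the cohort fixes the dose and only lasmiditan versus placebo is randomised, which is how 5.1 and 5.4 read. The two do not sit together easily: an allocation on Day 1 that also set the dose would spread arriving subjects over all doses, so cohorts could not be run one after another. The tablet count would also reveal membership of the 200 mg cohort.

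The point touches the primary objective. Among lasmiditan subjects, dose and cohort coincide completely, so the power model cannot separate a cohort or calendar effect from a dose effect. Only random allocation to dose would protect the 200:50 mg ratio. Likewise, only 2 of the 6 pooled placebo subjects come from the same cohort as any given dose, and under sequential dosing the other 4 would not be concurrent. A reader who sees the word randomised in the design description might take these comparisons to be randomised.

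**Working it through.** **1. The plan's own figure.** 3 cohorts × (10 + 2) = 36 subjects, of whom 30 receive lasmiditan and 6 placebo. This agrees with Protocol 5.2.

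**2. The passages side by side.**
- Protocol 5.1: the cohort carries the dose and the 10:2 split lies inside it. This points to randomisation within cohort.
- Protocol 5.4: cohorts may run in sequence. This points the same way.
- Protocol 5.2 names enrolment and randomisation together, so it is neutral. Appendix 1 defines enrolling as assigning to a treatment, without saying whether at random, so it does not separate the readings.
- Protocol 7.2: treatment groups can mean lasmiditan or placebo within a cohort, or all four treatments. It is ambiguous.
- SAP section 6 sets names and column order for tables. It is neutral.
- Protocol 9.2 is the one phrase that, taken literally, makes dose itself randomised. It fits the other reading if it means the cohort's dose or placebo.
- Protocol 7.3 and the tablet counts agree if the blind covers lasmiditan versus placebo. The scope of the blind is left to the Blinding Plan, which is not part of the documents reviewed.

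Most of the text tells one story. Random allocation to cohort is not excluded if the cohorts run in parallel.

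**3. How a cohort difference enters the ratio.** Put x = log2(dose/100) = −1, 0, 1. The log 200:50 ratio is 2 × slope, so cohort i has weight 2·n_i·(x_i − x̄)/Sxx. With equal numbers the weights are −1, 0 and +1. Over all combinations of 8 to 10 evaluable subjects per dose, the 100 mg weight is at most 0.08 in absolute value: n = (8, 10, 10) gives −0.96, −0.08 and 1.04. Only a difference between the 50 mg and 200 mg cohorts matters.

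**4. Size under assumptions.** The documents give no CV and no estimate of a cohort difference, so both are assumed here. With s = √ln(1 + CV²) and SE = s·√(2/n), CVs of 20%, 35% and 50% give SE = 0.089, 0.152 and 0.211 for n = 10, and 0.099, 0.170 and 0.236 for n = 8. For a proportional cohort difference d, coverage of the nominal 90% interval comes from the noncentral t distribution with 3n − 2 degrees of freedom and noncentrality ln(1 + d)/SE.

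| Assumed d | n per dose | CV 20% | CV 35% | CV 50% |
|---|---|---|---|---|
| 2% | 10 | 89.2% | 89.7% | 89.9% |
| 2% | 8 | 89.4% | 89.8% | 89.9% |
| 5% | 10 | 85.1% | 88.3% | 89.1% |
| 5% | 8 | 86.2% | 88.7% | 89.3% |
| 10% | 10 | 72.0% | 83.7% | 86.7% |
| 10% | 8 | 75.7% | 85.0% | 87.4% |

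For scale, at CV 35% and 10 per dose the interval runs from the estimate divided by 1.30 to the estimate multiplied by 1.30: exp(1.701 × 0.152) = 1.295. A 10% shift lies well inside that width.

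**5. What clarification would change.** If the cohort is set at enrolment, stating so leaves allocation, the power model, estimates, intervals and tables the same. Only a descriptive remark is added.

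**The case for a change.** The best case for acting is that the primary objective is PK, that the 200:50 mg ratio is its only planned inferential result, and that a descriptive estimate still needs a correct description. The study is called randomised and placebo-controlled, Protocol 9.2 literally ties dose to randomisation, and nothing in the SAP warns that between-dose contrasts may not be randomised. The remedy would be a few sentences.

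Part of this stands. The phrase in 9.2 and the silence of 7.2 on cohorts are imprecise, and dose and cohort cannot be separated in the model. The rest is weaker. Protocol 5.4 says that the randomised, placebo-controlled design is there to limit bias in the safety and tolerability objective; it claims no such protection for dose proportionality. Lasmiditan versus placebo within a cohort is randomised under either reading. No passage presents the ratio as a randomised contrast, so no stated claim is false. Each dose against pooled placebo is a set of descriptive columns. Eligibility, fasting and meal rules and the assay are common to all cohorts, and no concrete source of a cohort difference has been identified.

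**Conclusion.** The mismatch in wording is real but minor. Protocol 5.1 and 5.4 indicate that dose follows the cohort and that the 10:2 randomisation is within cohort; 7.2 leaves this unsaid and 9.2 words it loosely. An analyst can carry out SAP 9.3.2 in full without settling the point, and can note in the study report that between-dose comparisons are descriptive and, if it proves so, non-randomised.

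No planned estimate, interval, table or decision depends on it: the ratio has no acceptance limit, and Protocol 10.1 states that the study is not powered for hypothesis testing. The loss of coverage shown, to 72% at the worst and to about 90% at the mildest, rests wholly on assumed CVs of 20% to 50% and assumed cohort differences of 2% to 10%. The documents give no evidence of such a difference. The conclusion assumes that cohort is set at enrolment, as the design text suggests; if dose is in fact randomised, the concern about the ratio falls away.
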